## 6.1 Study Intervention(s) Administered

**Table 1 – Treatments administered**

Treatment (condition)	Dose / route	Amount / form	Frequency of administration
Naproxen sodium and caffeine CCI (postsurgery)	CCI / orally	CC tablet*	single dose
Naproxen sodium and caffeine CCI (postsurgery)	CCI / orally	CC tablet*	single dose
Naproxen sodium and caffeine CCI (postsurgery)	CCI / orally	CCI tablets	single dose
Naproxen sodium and caffeine CCI (postsurgery)	CCI / orally	CCI tablets	single dose
Naproxen sodium CCI (postsurgery)	CCI / orally	CCI tablet*	single dose
Caffeine CCI (postsurgery)	CCI / orally	CCI tablets	single dose
Placebo (postsurgery)	NA / orally	2 / tablets	single dose

\*participants assigned to these study interventions will also receive a second tablet of placebo so that blinding is maintained.

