While caffeine may affect various physiological processes, its main mode of action is through antagonism of adenosine receptors in the brain. The reduction in adenosine activity results in increased activity of dopamine, largely accounting for the stimulatory effect of caffeine. Caffeine can also exhibit mood enhancing properties (Sawynok and Yaksh 1993).

CCI

This dose ranging study is intended to find the minimum effective dose of caffeine to potentiate the analgesic effect of naproxen sodium.

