## 4.3 Justification for Dose of Active Treatment Groups

Participants will receive a single dose of study intervention, in order to provide an analgesic effect in participants who experience post-surgical dental pain.

The recommended amount of naproxen sodium in the new fixed dose combination product is based on currently marketed Aleve. Its safety and efficacy is well characterized throughout more than 20 years of use in the over-the-counter setting.

The amounts of caffeine to be tested in this dose ranging study are based on

CCI

Current marketed analgesic combination products of caffeine with acetaminophen or aspirin (e.g. Excedrin), recommend a dose

CCI

CCI A newly marketed fixed dose combination ibuprofen plus caffeine product in Europe

CCI

In the monograph for OTC stimulant drug products the dosage for caffeine is 100-200 mg every 3-4 hours, which can reach 600-1600 mg daily. Existing caffeine products in the market have 200 mg per dose as a stimulant (NoDoz, Vivarin). In the monograph for OTC menstrual drug products (21 CFR 357), caffeine is dosed at 100-200 mg when used as a diuretic. This monograph also indicates that while the amount of caffeine leading to nervousness and excitability varies greatly among individuals, 100-200 mg does not induce such negative effects for most people. Furthermore, caffeine is commonly consumed in beverages such as coffee (100-150 mg/cup), tea (75 mg/cup), cola (40 mg/drink) and energy drinks (80 mg/drink).

It is anticipated that a caffeine dose of [REDACTED] will not show a potentiation of effect of naproxen sodium, as was observed in studies with other analgesics, and particularly with [REDACTED]

Taking [REDACTED] the proposed product with [REDACTED] caffeine per tablet will add up to only [REDACTED] caffeine if the consumer takes [REDACTED]. A limit of [REDACTED] of caffeine per day. Therefore, the use of [REDACTED] caffeine as proposed in each tablet of this fixed dose combination product is well below the currently permitted limits in the relevant OTC drug monographs and should not pose any safety concerns. Its efficacy and safety will be evaluated through the proposed studies.

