**Table 2 – Identity of study treatment**

Treatment (UI)	Naproxen / Caffeine	Naproxen / Caffeine	Naproxen	Caffeine	Placebo
	CCI	CCI	CCI	CCI	CCI
Dose	CCI	CCI	CCI	CCI	CCI
Pharmaceutical Form	tablet	tablet	tablet	tablet	tablet
Strength	CCI	CCI	CCI	CCI	not applicable
Formulation	naproxen sodium caffeine microcrystalline cellulose copovidone talc magnesium stearate blue film coating	naproxen sodium caffeine microcrystalline cellulose copovidone talc magnesium stearate blue film coating	naproxen sodium FD&C blue #2 lake hypromellose magnesium stearate microcrystalline cellulose polyethylene glycol povidone talc titanium dioxide	caffeine microcrystalline cellulose colloidal silicon dioxide magnesium stearate blue film coating	dibasic calcium phosphate dihydrate magnesium stearate microcrystalline cellulose blue film coating
Route of administration	orally with a full glass of water (i.e. about 8 ounces or 240 mL)	orally with a full glass of water (i.e. about 8 ounces or 240 mL)	orally with a full glass of water (i.e. about 8 ounces or 240 mL)	orally with a full glass of water (i.e. about 8 ounces or 240 mL)	orally with a full glass of water (i.e. about 8 ounces or 240 mL)
Batch Number	see study file	see study file	see study file	see study file	see study file
Trade Name and Manufacturer	Bayer Morristown, NJ USA	Bayer Morristown, NJ USA	Aleve® Bayer Bitterfeld, Germany	Bayer Morristown, NJ USA	Bayer Morristown, NJ USA

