### 6.1.1 Study intervention assignment

At the beginning of the first treatment period, after completion of the pre-treatment baseline procedures/assessments, participants who meet the entry criteria will be sequentially assigned to a unique number in sequential order (randomization number, RNR) according to the randomization schedule 2:2:2:2:2:1:1 (naproxen sodium/caffeine [CCI], naproxen sodium/caffeine [CCI]; naproxen sodium [CCI], naproxen sodium/caffeine [CCI], naproxen sodium [CCI]; caffeine [CCI]; placebo) prepared prior to the study.

Participants will be numbered according to the following scheme:

[PPD]

Whereas the “Xs” will be replaced with a four digit sequentially assigned number as each participant enters the study (e.g., first participant number will be [PPD]).

The unique participant identifier number will be assigned in numerical order prior to dosing. Participants who characterize their pain severity as *mild* and <5 on the NRS will not receive treatment and be withdrawn from the study.

Once a number has been assigned to a participant, it cannot be reassigned to another participant.

Participants completing the Screening Visit, if not scheduled for surgery the same day, will return to the trial site within 28 days, and if they continue to meet inclusion/exclusion criteria post-surgery will be randomized to one of seven treatment groups:

- naproxen sodium/caffeine [CCI]
- naproxen sodium/caffeine [CCI]
- naproxen sodium/caffeine [CCI]
- naproxen sodium/caffeine [CCI]
- naproxen sodium [CCI]
- caffeine [CCI]
- placebo (2 tablets)

Participants will be assigned to treatment groups in accordance with the randomization schedule. The Sponsor will provide a randomization schedule to the study site.

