## 6.3 Measures to Minimize Bias: Randomization and Blinding

On Day 1, participants will be assigned a unique number (randomization number) in ascending numerical order at the study site. The randomization number encodes the participant's assignment to one of the seven (7) arms of the study, according to the randomization schedule generated prior to the study by the Sponsor. Each participant will be dispensed blinded study intervention, labeled with his/her unique randomization number, throughout the study.

Participants enrolled in the trial, investigators and their staff involved in protocol procedures or who are involved in data collection, data entry and data analysis will be blinded to the

identity of the treatments until the database is locked. The study monitor will conduct product accountability after database lock. To preserve blinding, participants will be blindfolded during administration of study medication. Study drug will be dispensed by an unblinded study team member based on the randomization schedule. That team member may have no other role in the study conduct and may not reveal the study drug's identity to any members of the blinded study team.

Sponsor will supply study medication in bulk containers. Selection of the proper dose for an individual participant will be performed by an unblinded study team member using the provided randomization schedule. The unblinded study team member will withdraw the appropriate study medication from the bulk container and transfer it to a dispensing cup. All study interventions must be administered as 2 tablets per participant. Some study interventions require the addition of a placebo tablet. The unblinded study team member will then bring the study medication to the treatment room where it will be dispensed to the participant by the study team member. The unblinded study team member should have no other responsibilities in the study.

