#### 9.4.1 Efficacy Analyses

For each post-dose time point, Pain Intensity Differences (PID) will be derived by subtracting the pain intensity at the post-dose time point from the baseline intensity score (baseline score – post-baseline score). A positive difference is indicative of improvement. Time-weighted Sum of Pain Intensity Differences (SPIDs) will be calculated for 2, 4, 8, and 12 hours by

multiplying the PID score at each post-dose time point by the duration (in hours) since the preceding time point and then summing these values over 2, 4, 8, and 12 hours, respectively.

Similarly, Total Pain Relief Scores (TOTPARs), will be calculated by multiplying the pain relief score at each post-dose time point by the duration (in hours) since the preceding time point and then summing these values.

In all analyses for participants who take rescue medication, all pain intensity scores after intake of rescue medication will be imputed by the worse of the baseline or the score assessed immediately before taking rescue medication. All pain relief after intake of rescue medication will be imputed by “no relief” (0).

Endpoint	Statistical Analysis Methods
Primary	
The primary efficacy analyses population will be based on the PP population.
 
Sum of Pain Intensity Difference over 8 hours: SPID0-8 be analyzed using an analysis of covariance model (ANCOVA) with treatment as fixed effect and baseline pain intensity score as the covariate. A 95% of confidence interval (CI) for the treatment differences and pairwise p-values will be calculated based on the above mentioned model.

Secondary	
Total Pain Relief over 8 hours: TOTPAR0-8 will be analyzed similarly as for the primary endpoint.
 
Time to first use of rescue medication. If a participant did not take the rescue medication during the treatment period, (s)he will be censored at the time of last assessment. Time to first use of rescue medication will be estimated and plotted using Kaplan-Meier method and analyzed using log-rank test.

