2.2 Study Rationale

CCI

This study is intended to find the optimal dose for caffeine to be added to CCI naproxen sodium in a single tablet. This study will also compare the analgesic efficacy of CCI

CCI

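### Does the plan need to state which FDC-versus-naproxen contrasts isolate caffeine, given that some FDC arms may carry a different amount of naproxen from the control?

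*Protocol*

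**What the plan says.** **Tablets.** In Protocol Table 1, two FDC rows and the naproxen-only row are asterisked and singular, with the footnote "participants assigned to these study interventions will also receive a second tablet of placebo so that blinding is maintained". The remaining two FDC rows and the caffeine row are plural and unmarked, with the counts blacked out. Protocol 6.3 adds: "All study interventions must be administered as 2 tablets per participant". Table 2 has two FDC products, one naproxen tablet ("Aleve® Bayer Bitterfeld, Germany"), one caffeine tablet and one placebo, with strengths blacked out. Protocol 4.3 says "The recommended amount of naproxen sodium in the new fixed dose combination product is based on currently marketed Aleve", and no figure is visible.

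**Purpose.** Protocol 2.2: "This dose ranging study is intended to find the minimum effective dose of caffeine to potentiate the analgesic effect of naproxen sodium". SAP 2.2: "This study is intended to find the optimal dose for caffeine to be added to CCI naproxen sodium in a single tablet". The sentence after that one announces a further efficacy comparison whose terms are blacked out. A partly redacted secondary objective (Protocol 1.1 and 3) compares caffeine dosing within the FDC product.

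**Analysis.** Protocol 9.4.1 fits an ANCOVA to SPID0-8 with treatment and baseline pain intensity, and then: "A 95% of confidence interval (CI) for the treatment differences and pairwise p-values will be calculated based on the above mentioned model". No particular contrast is singled out. Protocol 9 leaves the fuller methodology to the SAP. There, the body of 6.1.1, nearly all of 6.8, the part of 6.8.1 after the endpoint derivation, and part of section 8 are redacted.

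**Arm list.** The schedule sentence in Protocol 6.1.1 ends "naproxen sodium [CCI], naproxen sodium/caffeine [CCI], naproxen sodium [CCI]; caffeine [CCI]; placebo) prepared prior to the study". Read literally with the words before it, it has three FDC and two naproxen-only entries.

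**The concern.** The study exists to learn what caffeine adds to naproxen. An FDC-minus-naproxen difference answers that only when both arms contain the same naproxen. Two tablets of a product hold twice what one tablet holds, so one-tablet and two-tablet arms of the same product cannot both equal a single control.

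The visible primary analysis lists pairwise comparisons without separating matched from unmatched ones. Neither randomisation nor covariate adjustment helps, because the difference in naproxen is part of the treatment definition. A reader could credit caffeine with an effect that belongs to extra naproxen, or miss a caffeine effect hidden by less naproxen. A second naproxen-only arm, as the 6.1.1 sentence seems to imply, would also change which contrasts are matched.

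**Working it through.** **1. The plan's own numbers.** Seven arms at 2:2:2:2:2:1:1 (Protocol 6.1.1) with a unit of 15 give 15 × 12 = 180. At 5% dropout, 180 / 0.95 = 189.5, rounded up to 190. Both figures reproduce. The six-term ratio printed in 9.2 gives 15 × 10 = 150, so one term was dropped in printing. Each FDC arm and the naproxen-only arm has 30 evaluable participants.

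**2. How many FDC arms can match.** Let a and b be the naproxen per tablet in the two FDC products (both above zero) and N the control's naproxen. The one-tablet arms contain a and b. If the unmarked arms are two FDC tablets, they contain two of {2a, 2b, a+b}.

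- Pair 2a and 2b: a and 2a cannot both be N, and neither can b and 2b. Maximum 2 matched.
- Pair 2a and a+b (2b and a+b is the mirror image): a+b exceeds both a and b. If a+b = N, neither one-tablet arm matches, which leaves at most 2. If a+b ≠ N, the candidates are a, b and 2a, and a and 2a exclude each other. Maximum 2.

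The bound of 2 in 4 does not depend on the strengths. Which two arms match does:

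| Strengths | Matched | Unmatched |
|---|---|---|
| a = b = N | both one-tablet arms | both two-tablet arms, at 2N |
| a = b = N/2 | both two-tablet arms | both one-tablet arms, at N/2 |
| b = 2a = N (pair 2a, 2b) | one of each | one at N/2, one at 2N |

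The bound does depend on the tablet reading. If an unmarked arm were one FDC tablet plus one caffeine tablet, the four arms would contain a, b, a, b, and all 4 could match when a = b = N. No visible text describes such a pairing. The redacted counts do not rule it out.

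**3. Size if a contrast is unmatched.** For 30 against 30, SE = √(1/30 + 1/30) = 0.258 SD. Error df = 180 − 7 − 1 = 172, the critical t is 1.974, and the 95% half-width is 1.974 × 0.258 = 0.51 SD. Take a zero caffeine effect and a naproxen difference worth δ SD. The chance of significance in the FDC's favour (two-sided 0.05) is the probability that a noncentral t with 172 df and noncentrality ±δ/0.258 exceeds 1.974. The documents give no δ, so the range is assumed. The last column is from 1,000,000 simulations with a shared control.

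| δ (SD) | Arm has more naproxen | Arm has less naproxen | At least one of two, both with more |
|---|---|---|---|
| 0 | 2.5% | 2.5% | 4.5% |
| 0.1 | 5.8% | 1.0% | 10.0% |
| 0.2 | 11.7% | 0.3% | 19.3% |
| 0.3 | 21.1% | 0.1% | 32.7% |
| 0.5 | 48.6% | below 0.1% | 65.3% |

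The last column applies only to the first row of the strengths table. In the third row one contrast is pushed each way, and in the second both are pushed against the FDC.

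**4. What a label would change.** The ANCOVA uses treatment assignment and baseline pain. Naming some contrasts as the caffeine evidence leaves every mean difference, interval and p-value as it was.

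**5. The arm list.** Four FDC arms and one naproxen-only arm appear in the synopsis, Figure 1, Table 1, the bullets of Protocol 6.1.1 itself, and the SAP 4.1 figure. Only the schedule sentence departs from this. Under either count five arms carry weight 2, so the ratio and the 180 are unaffected.

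**The case for a change.** The best case for a change is that it is cheap and that part of the protocol is not hidden. Sections 9.1 and the primary row of 9.4.1 show no redaction and name no contrast. The primary objective speaks of the FDC as if it were one treatment. The two-tablet reading is well supported by Table 1, Table 2 and the two-tablet rule taken together, and the bound then needs no redacted figure. Being unpowered is no excuse when choosing a caffeine dose is the purpose. Two sentences would remove the ambiguity.

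Most of the reasoning stands: the bound is correct on its condition, and an unmatched contrast cannot by itself show what caffeine contributes. The inference that the plan lacks this distinction does not stand. Arm names in the public copy stop where the contents would be, and the SAP sections where the model and comparisons belong are almost entirely blacked out. The redacted secondary comparison may be what the two-tablet arms are for. No visible sentence claims that all four FDC-versus-naproxen contrasts are evidence for caffeine, and no visible success rule turns one significant pairwise p-value into such a claim.

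The suggestion that the two-tablet arms hold twice the control's naproxen rests on the Aleve wording in Protocol 4.3 and Table 2, which points that way without stating it.

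A contrast of higher against lower FDC strength, averaged within tablet count, would have SE √(1/60 + 1/60) = 0.183 SD instead of 0.258. It presumes a layout that cannot be seen, has no zero-caffeine reference, and may already be planned.

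**Conclusion.** No change to the plan follows. If the two unmarked FDC arms are two FDC tablets each, at least 2 of the 4 FDC-versus-naproxen contrasts differ in naproxen as well as caffeine. Misattribution could then be appreciable: 6% to 49% per contrast for 0.1 to 0.5 SD of extra naproxen, against a nominal 2.5%. Those figures assume no caffeine effect, 30 per arm, a two-sided 0.05 test and more naproxen in the FDC arm. With less naproxen they fall to 1% or below.

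The distinction is one of interpretation. Anyone holding the unredacted arm contents can make it by comparing naproxen amounts, and writing it down would move no result. The public text cannot show that it is absent. The 6.1.1 schedule sentence is a clerical slip to be reconciled with the five consistent listings, and it does not bear on the analysis. The most that remains is a question to the sponsor: does the unredacted text identify the naproxen-matched contrasts?

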**Table 2 – Identity of study treatment**

Treatment (UI)	Naproxen / Caffeine	Naproxen / Caffeine	Naproxen	Caffeine	Placebo
	CCI	CCI	CCI	CCI	CCI
Dose	CCI	CCI	CCI	CCI	CCI
Pharmaceutical Form	tablet	tablet	tablet	tablet	tablet
Strength	CCI	CCI	CCI	CCI	not applicable
Formulation	naproxen sodium caffeine microcrystalline cellulose copovidone talc magnesium stearate blue film coating	naproxen sodium caffeine microcrystalline cellulose copovidone talc magnesium stearate blue film coating	naproxen sodium FD&C blue #2 lake hypromellose magnesium stearate microcrystalline cellulose polyethylene glycol povidone talc titanium dioxide	caffeine microcrystalline cellulose colloidal silicon dioxide magnesium stearate blue film coating	dibasic calcium phosphate dihydrate magnesium stearate microcrystalline cellulose blue film coating
Route of administration	orally with a full glass of water (i.e. about 8 ounces or 240 mL)	orally with a full glass of water (i.e. about 8 ounces or 240 mL)	orally with a full glass of water (i.e. about 8 ounces or 240 mL)	orally with a full glass of water (i.e. about 8 ounces or 240 mL)	orally with a full glass of water (i.e. about 8 ounces or 240 mL)
Batch Number	see study file	see study file	see study file	see study file	see study file
Trade Name and Manufacturer	Bayer Morristown, NJ USA	Bayer Morristown, NJ USA	Aleve® Bayer Bitterfeld, Germany	Bayer Morristown, NJ USA	Bayer Morristown, NJ USA

### 6.1.1 Study intervention assignment

At the beginning of the first treatment period, after completion of the pre-treatment baseline procedures/assessments, participants who meet the entry criteria will be sequentially assigned to a unique number in sequential order (randomization number, RNR) according to the randomization schedule 2:2:2:2:2:1:1 (naproxen sodium/caffeine [CCI], naproxen sodium/caffeine [CCI]; naproxen sodium [CCI], naproxen sodium/caffeine [CCI], naproxen sodium [CCI]; caffeine [CCI]; placebo) prepared prior to the study.

Participants will be numbered according to the following scheme:

[PPD]

Whereas the “Xs” will be replaced with a four digit sequentially assigned number as each participant enters the study (e.g., first participant number will be [PPD]).

The unique participant identifier number will be assigned in numerical order prior to dosing. Participants who characterize their pain severity as *mild* and <5 on the NRS will not receive treatment and be withdrawn from the study.

Once a number has been assigned to a participant, it cannot be reassigned to another participant.

Participants completing the Screening Visit, if not scheduled for surgery the same day, will return to the trial site within 28 days, and if they continue to meet inclusion/exclusion criteria post-surgery will be randomized to one of seven treatment groups:

- naproxen sodium/caffeine [CCI]
- naproxen sodium/caffeine [CCI]
- naproxen sodium/caffeine [CCI]
- naproxen sodium/caffeine [CCI]
- naproxen sodium [CCI]
- caffeine [CCI]
- placebo (2 tablets)

Participants will be assigned to treatment groups in accordance with the randomization schedule. The Sponsor will provide a randomization schedule to the study site.

### 6.1.2 Participant Administration

Each participant will receive a single dose of the investigational medicinal product (IMP). Participants receive the IMP with a full glass of non-refrigerated, non-carbonated water (about 8 ounces or 240 mL). Study intervention will be administered using dosing cups. Selection and preparation of the proper dose will be performed by an unblinded study team member using the provided randomization schedule (see Section 6.3). The Investigator or a designee will supervise the study intervention administration in a manner, which maintains the masking conditions (blinding of the participant).

Participants must be nil per os (NPO) from midnight prior to surgery until completion of surgery. Each participant will continue fasting, with the exception of clear liquids, until after study drug administration.

## 6.2 Preparation/Handling/Storage/Accountability

All study drugs will be labeled according to the requirements of local law and legislation. Label text will be approved according to the sponsor's agreed procedures, and a copy of the labels will be made available to the study site upon request.

For all study drugs, a system of numbering in accordance with all requirements of Good Manufacturing Practice (GMP) will be used, ensuring that each dose of study drug can be traced back to the respective bulk batch of the ingredients. Lists linking all numbering levels will be maintained by the sponsor's clinical supplies Quality Assurance (QA) group.

A complete record of batch numbers and expiry dates of all investigational products as well as the labels will be maintained in the clinical supply file.

The source of test and reference products will be documented in the clinical supply file.

The investigator or designee must confirm appropriate temperature conditions have been maintained during transit for all study intervention received and any discrepancies are reported and resolved before use of the study intervention. Only participants enrolled in the study may receive study intervention and only authorized site staff may supply or administer study intervention. All study intervention must be stored in a secure, environmentally controlled, and monitored (manual or automated) area in accordance with the labeled storage conditions with access limited to the investigator and authorized site staff. The investigator, institution, or the head of the medical institution (where applicable) is responsible for study intervention accountability, reconciliation, and record maintenance (i.e., receipt, reconciliation, and final disposition records).

The Sponsor will provide sufficient quantity of the IMP to the study site. The study center will dispense IMP according to the randomization schedule and the participant's categorical pain intensity (moderate or severe) post-surgery. IMP will be supplied to the study center in multi-dose bottles and dispensed by an unblinded member of the study team.

All study drugs will be stored at the investigational site in accordance with GCP requirements and the instructions given by the clinical supplies department of the sponsor (or its affiliate/CRO), and will be inaccessible to unauthorized personnel. Special storage conditions and a complete record of batch numbers and expiry dates can be found in the Sponsor's study file; the site-relevant elements of this information will be available in the investigator site file. On the day of receipt, the responsible site personnel will confirm receipt of study investigational products in writing. The personnel will use the study investigational products only within the framework of this clinical study and in accordance with this protocol. Receipt, distribution, return and destruction (if any) of the study drug must be properly documented according to the sponsor's agreed and specified procedures.

